10.7. Physical and Neurologic Assessments

10.7.1. Physical Examinations

A complete physical examination will include, at a minimum, assessments of the cardiovascular, respiratory, gastrointestinal, musculoskeletal, and neurological systems.

A targeted physical examination will include, at a minimum, assessments of the skin, lungs, cardiovascular system, and abdomen (liver and spleen). Investigators should pay special attention to clinical signs related to previous serious illnesses.

Weight will also be measured and recorded during both complete and targeted physical exams.

10.7.2. Focused Neurological Examinations

A focused neurologic examination, including an assessment of spinal and cranial nerves, will be conducted by a clinician with appropriate training at timepoints indicated in the Schedule of Events (Table 3). Any abnormalities will be recorded.

10.7.3. Audiometry

A hearing test will be performed at time points specified in Table 3. Additional details regarding audiometry assessment are available in the Study Reference Manual.

10.7.4. Dental Health Assessment

A dental health assessment will be performed at time points specified in Table 3. Dental health assessment includes assessing for any potential confounding effects of prior bisphosphonate exposure or risk factors for osteonecrosis of the jaw.

10.8. Appropriateness of Measurements

The efficacy endpoints to be evaluated in this study examine treatment effects on skeletal health. Fractures are a hallmark of OI, and reduction of fracture incidence is an important treatment goal. Therefore, assessments include radiographic evaluation of fracture incidence and assessment of BMD to determine whether potential increases in BMD with treatment correspond with a reduction in fracture incidence. Bone formation and resorption markers will also be assessed as indicators of treatment effect on bone health. Patient/caregiver- and clinician-reported outcomes have been included to further inform treatment benefits on key disease manifestations and symptoms as perceived by the patient or their caregiver/clinician.

The safety parameters to be evaluated in this study include standard safety assessments such as recording medical history, AEs, SAEs, physical examination, vital signs, serum chemistry, concomitant medication, and other clinical and laboratory procedures. Additionally, subjects will be monitored for AESIs,

these

AESIs were defined based on safety data from prior clinical studies of setrusumab and product class information from other anti-sclerostin antibodies.

11. STATISTICAL CONSIDERATIONS

A full description of the analysis details will be provided in the Statistical Analysis Plan (SAP).

11.1. Sample Size Determination

As only subjects who participated in the ASTEROID study are eligible, the sample size for this study is limited to the number of subjects who participated in ASTEROID and not driven by hypothesis testing. Assuming % recruitment failure rate from the ASTEROID study and % dropout rate by Month $1\overline{2}$ of the Retreatment Period, there will be around subjects with data at Month 12. For the primary endpoint of percentage change from Retreatment Baseline in lumbar spine BMD measured by DXA at Month 12 of the Retreatment Period, assuming the percentage change from Month 0 of the Retreatment Period (Retreatment Baseline) in lumbar spine BMD at Month 12 of CC , a sample size of around subjects will provide greater than work power to detect the change from baseline at 1-sided significance level of CC. For the secondary endpoint of percentage change from Retreatment Baseline in total hip BMD at Month 12 of the Retreatment Period, assuming the percentage change from Month 0 of the Retreatment Period (Retreatment Baseline) in total hip BMD at Month 12 of , a sample size of around currently subjects will provide greater than % power to detect the change from baseline at 1-sided significance level of Analysis Sets

For the purposes of analysis, the analysis sets are defined in the SAP.

11.2. Planned Methods of Analysis

This section is a summary of the planned statistical analyses of the most important endpoints including primary and key secondary endpoints.

11.2.1. General Principles

A general description of the statistical methods to be used to analyze the study endpoints is outlined below. The analyses planned in this protocol will be expanded in the SAP to include detailed description of the analyses.

The statistical analyses will be reported using summary tables, figures, and data listings. Descriptive statistics for continuous variables will include number of patients (n), mean, standard deviation (SD), median, minimum, and maximum, unless otherwise noted. Frequency and percentage will be calculated for categorical variables.

11.2.2. Efficacy Analyses

11.2.2.1. Primary and Secondary Efficacy Endpoints

The primary endpoint, percentage change from Retreatment Baseline in lumbar spine BMD measured by DXA at Month 12 of the Retreatment Period will be analyzed using a mixed-effects model for repeated measures that includes visit as a categorical variable and adjusted for baseline measurement. Other covariates may be considered. Model-based estimates of the percentage changes from baseline and corresponding of confidence intervals will be provided along with p-values.

The secondary endpoint, percentage change from Retreatment Baseline in total hip BMD measured by DXA at Month 12 of the Retreatment Period, will be analyzed similarly to lumbar spine BMD as described above.

The other secondary endpoint, number of fractures (total and by fracture type) and proportion of subjects who experience a fracture, as confirmed by radiograph during the Retreatment Period, will be summarized descriptively. The annualized new fracture rate during Retreatment Period will be compared with the annualized fracture rate during the Observational Period and\or Off-study Period using a generalized linear mixed effect model.

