During the Retreatment Screening Visit subjects undergo screening to confirm eligibility for retreatment with setrusumab, including an assessment of serum calcium and 25-OH-vitamin D (Section 8.2 and Section 8.5). If a Visit occurred within 4 weeks prior to the Retreatment Baseline, then safety laboratory tests do not need to be recollected at the Retreatment Screening Visit, except for the chemistry panel, which is collected at both the Retreatment Screening Visit and Retreatment Baseline.

The dosing strategy in the Retreatment and Extension Periods will be based on the pharmacokinetic (PK) and serum bone turnover markers from the Phase 2b ASTEROID study and the Phase 2 Period of the UX143-CL301 study. The selected dose will be in the range of 20 to 40 mg/kg CC

During the single-arm Retreatment Period, subjects receive open-label setrusumab QM for 12 months. During the Retreatment Period, subjects are assessed for safety and efficacy of

Following the Retreatment Period, subjects enter an Extension Period, in which they are randomized 1:1 to either continue treatment with open-label setrusumab QM or transition to open-label setrusumab CC for at least 12 months or until setrusumab is commercially available. For the Extension Period dosing groups, randomization will be stratified by OI type (I vs III/IV).

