7.1.2. Number of Subjects

Up to 112 subjects will be enrolled; only those who participated in ASTEROID.

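### The model-based interval for the single-arm mean BMD change may be somewhat too narrow, because its standard error treats baseline as fixed if percentage change depends on baseline

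*Combined protocol and SAP*

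**What the plan says.** Section 7.1 describes the analysed period: "During the single-arm Retreatment Period, subjects receive open-label setrusumab QM for 12 months". There is no concurrent control, so the primary quantity is a mean, not a difference between arms.

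Section 11.2.2.1 analyses percentage change in lumbar spine BMD with a "mixed-effects model for repeated measures that includes visit as a categorical variable and adjusted for baseline measurement". On reporting it says: "Model-based estimates of the percentage changes from baseline and corresponding of confidence intervals will be provided along with p-values". It adds that "Other covariates may be considered", and it treats total hip BMD in the same way. Table 7 states the objective for adults with OI in general and fixes no baseline value. Table 3 schedules DXA at Months 0, 6 and 12 of the Retreatment Period.

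The text does not give the baseline value at which the Month 12 mean is evaluated, the variance estimator, or whether the baseline slope may differ by visit. Section 11 defers: "A full description of the analysis details will be provided in the Statistical Analysis Plan (SAP". The supplied document contains no separate SAP text. In section 11.1 the evaluable number, assumed change, power and significance level are redacted, and that is not a fault of the plan.

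**The concern.** With baseline as a covariate, the reported mean is normally the fitted value at the sample mean baseline. With complete data that fitted value is the raw mean. Its model standard error, however, uses the residual SD after removing the part explained by baseline. Estimating the mean in adults with OI also carries the chance variation of the sampled baselines. In a two-arm difference that component largely cancels; in a single arm it does not.

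If percentage change depends on baseline, adjustment therefore leaves the estimate where it was and shortens its interval, and the apparent gain in precision is not real. What is at stake is the stated coverage of the primary interval and of the total hip interval. Any further prognostic covariate would enlarge the omitted component.

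**Working it through.** **Inputs.** From the documents: single arm, repeated-measures model adjusted for baseline, model-based intervals, at most 112 subjects ("Up to 112 subjects will be enrolled; only those who participated in ASTEROID"). Assumed, because redacted or not given: 95% confidence, 60 to 80 evaluable subjects at Month 12, evaluation at the observed mean baseline, and everything about the baseline distribution and the gain. The plan has no visible figure to reproduce.

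**Formula.** Let r be the correlation of Month 12 percentage change Y with baseline X, and β the slope.

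- Model variance of the mean: Var(Y)(1 − r²)/n.
- Omitted term: β²Var(X)/n. Since β²Var(X) = r²Var(Y), this equals r²Var(Y)/n.
- Sum: Var(Y)/n, the one-sample variance.
- Ratio of model SE to full SE: √(1 − r²).
- Coverage of a nominal 95% interval: 2Φ(1.96√(1 − r²)) − 1.

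| \|r\| | SE ratio | SE too small by | Widening once corrected | Coverage |
|---|---|---|---|---|
| 0 | 1.000 | 0% | 0% | 95.0% |
| 0.1 | 0.995 | 0.5% | 0.5% | 94.9% |
| 0.2 | 0.980 | 2.0% | 2.1% | 94.5% |
| 0.3 | 0.954 | 4.6% | 4.8% | 93.9% |
| 0.375 | 0.927 | 7.3% | 7.9% | 93.1% |
| 0.5 | 0.866 | 13.4% | 15.5% | 91.0% |

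**Check on the repeated-measures model.** Simulation with two visits, unstructured covariance, one common baseline slope, 10% missing at Month 12 and 2,000 trials per setting:

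- n = 60: SE ratio 0.99, 0.94, 0.86 at r = 0, 0.3, 0.5; coverage 94.4%, 93.6%, 91.8%.
- n = 80: SE ratio 1.00, 0.95, 0.88; coverage 94.8%, 93.6%, 91.6%.

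These agree with the formula.

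**What r might be.** Assume mean baseline 0.80 g/cm², baseline CV 15 to 25%, mean gain 4 to 8% with SD 5 to 8%, and 2% DXA error.

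- Percentage gain unrelated to baseline: r about −0.02 to −0.05, SE ratio about 1.00.
- Absolute gain unrelated to baseline: r about −0.10 to −0.38, SE ratio 0.995 to 0.93.

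A tighter spread of gains raises |r|. With n = 70 and absolute gain 0.06 g/cm² unrelated to baseline:

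- Baseline SD 0.12, gain SD 0.03: r about −0.30, coverage 94.2%.
- Baseline SD 0.20, gain SD 0.02 (0.02/0.80 = 2.5% of mean baseline): r about −0.60, coverage 88.6%.

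Adding β²Var(X)/n brought coverage back to 94.6 to 95.4%.

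**Behaviour under the null.** If absolute gain is unrelated to baseline, the expected percentage change at a given baseline is 100 × mean gain / baseline. At zero mean gain this is zero for every baseline, so the slope and the omitted term vanish. Simulated one-sided rejection at an assumed 2.5% was then about 2.3 to 2.8%.

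**The case against.** The strongest case against has five parts.

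- **The error is conditional.** It needs a non-zero slope, evaluation at the sample mean baseline, and the population mean as target. If the target is the mean at a pre-fixed baseline, the model interval is correct. This stands. A reader might infer that percentage change must correlate with its own baseline because baseline is its denominator. That does not follow: when gain is proportional to baseline, r is about zero, and the documents do not say which pattern holds.
- **Type I error.** A reader might also infer that the one-sided test rejects too often. Calculations showing this hold r at a non-zero value under the null, and the slope can vanish there. With 2% DXA error, simulated rejection was 2.9 to 3.2%, but alongside a small positive ratio bias (mean change 0.03 to 0.05%) that a different standard error does not remove. The objection stands.
- **The section is a summary.** Section 11.2 calls itself one, and detail is left to the SAP. Reading the absent baseline-by-visit term as a chosen common slope would be reading silence as a decision. The standard error is different: model-based intervals are stated, nothing in the supplied text signals a correction, and the ordinary default omits the term.
- **Little depends on it.** Section 11.1 says the sample size is "not driven by hypothesis testing", and no visible text ties a decision to the interval. With a gain of 0.06 g/cm², simulated mean/SE was about 13 to 25, so a modestly larger standard error would change no conclusion. This lowers the priority; it does not make the interval right.
- **Descriptive statistics may suffice.** Section 11.2.1 plans n, mean and SD, from which a reader could form the unadjusted interval. That helps only if they are shown for Month 12 percentage change, and the reported primary interval would still be the model's.

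**Conclusion.** The point holds conditionally. With the Month 12 mean evaluated at the observed mean baseline and a non-zero slope, the planned model-based interval is too narrow for the population mean change by a factor of about √(1 − r²). Neither r nor a baseline SD is in the documents, so the size is a range resting on the assumed inputs: about 0 to 7% of the standard error for |r| up to 0.38, and 13% or more only from |r| = 0.5. For a given non-zero slope the direction is always towards too much apparent precision. The documents support no claim of inflated one-sided type I error. Low priority, moderate confidence.

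**What to change.** In section 11.2.2.1 or the SAP:

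1. State that the target is the population mean percentage change at Month 12.
2. Keep the repeated-measures model and include a baseline-by-visit term, so that the Month 12 slope enters the calculation.
3. Compute the Month 12 standard error with baseline sampling included: add slope² × Var(baseline)/n to the model variance, bootstrap subjects, or model baseline as part of the response vector. If other covariates are added, the method must cover their sampling too.
4. Apply the same method to total hip BMD.

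The cost is a few lines of SAP wording and code, with no extra data or visits. Intervals widen by 1/√(1 − r²) − 1: under 1% at |r| = 0.1, about 5% at 0.3 and about 15% at 0.5. At r = 0 nothing material changes.

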11.2.2.2. Tertiary Efficacy Endpoints

11.3. Safety Analyses

Safety variables including all SAEs, TEAEs, AESIs, safety laboratory assessments, anti-setrusumab antibodies, vital signs, ECGs, physical examination, focused neurological examination, audiometry, and dental health assessments will be summarized descriptively and listed by subject.

All AEs will be coded according to the MedDRA Version 24.0 or above. The frequency and severity of all TEAEs, SAEs, AESIs and clinically relevant laboratory and ECG abnormalities reported as AEs will be reported by System Organ Class, Preferred Term, by severity, and by relationship to study drug, if applicable. All non-serious AEs reported with onset after the first dose of study drug (ie, TEAEs) will be included in the analysis. All SAEs will also be reported by relationship to study drug as reported by Investigator, seriousness criteria, timing, duration, and outcome. For all TEAEs; SAEs; AESIs; and treatment-related TEAEs, SAEs, and AESIs; the percentage of subjects who experienced at least 1 occurrence of the given event will be summarized. Data summaries and\or listings, and narratives will be provided for subjects who died, discontinued treatment or withdrew from study due to TEAE, or experienced SAEs, AESIs, and any study procedure-related AEs.

Clinical laboratory data changes from ASTEROID Baseline and Retreatment Baseline will be summarized by the type of laboratory test. Reference ranges and abnormal results (specified in the SAP) will be used in the summary of laboratory and ECG data. The frequency and percentage of subjects who experience abnormal clinical laboratory results (ie, outside of reference ranges) and/or clinically significant abnormalities (as determined by the Investigator) will be presented for each clinical laboratory measurement, including for Hy's Law analysis (alanine transaminase [ALT], aspartate aminotransferase [AST], total and direct bilirubin, alkaline phosphatase). Shift tables will be provided for changes from ASTEROID Baseline and Retreatment Baseline in selected chemistry and hematology laboratory parameters (if applicable). Listings of abnormal vital signs and physical findings will be provided (if applicable).

The SAP will provide additional details on the planned safety analyses.

11.4. Planned Analyses

The primary analysis is planned at the end of the Retreatment Period, reflecting 12 months of retreatment with setrusumab. No interim analyses are planned. The final analysis will be conducted at the end of the study.

11.5. Data Monitoring Committee

An independent DMC will be established with subject matter experts to serve in an advisory capacity to Ultragenyx.

The DMC will meet and review study data, including cardiovascular events and other AESIs, at the frequency defined and in accordance with the scope and objectives set forth in the DMC Charter. The DMC will provide advice to Ultragenyx regarding the safety of subjects, the ethics of the study and the continuing scientific validity of the study. The DMC may also make recommendations to Ultragenyx concerning continuation, termination or other modifications of

the study based on their review of data. Further details regarding the DMC can be found in the DMC charter.

Ultragenyx Data Review Board will review the DMC recommendations and determine necessary actions that will be communicated accordingly to all stakeholders, eg, Regulatory Authorities, IRB/IECs, and Investigators.

13. GENERAL APPENDICES

APPENDIX 1. SAFETY LABORATORY ASSESSMENTS

Table 10: Specified Laboratory Assessments

Chemistry	Hematology	Urinalysis
Alanine aminotransferase (ALT)	Hematocrit	Appearance
Alkaline phosphatase	Hemoglobin	Color
Amylase	Mean corpuscular hemoglobin (MCH)	рН
Aspartate aminotransferase (AST)	MCH concentration (MCHC)	Specific gravity
Bicarbonate (Total CO2)		
Bilirubin (direct and total)	Mean corpuscular volume (MCV)	
Blood urea nitrogen (BUN)	Platelet count	Bilirubin
Calcium	Red blood cell (RBC) count	Creatinine
Chloride	Reticulocyte count	Glucose
Cholesterol (total)	White blood cell (WBC) count	Hemoglobin
Creatine kinase	WBC differential:	Ketones
Creatinine	Basophil count (absolute and %)	Nitrite
Gamma-glutamyl transpeptidase (GGT)	Eosinophil count (absolute and %)	Protein
Glucose	Lymphocyte count (absolute and %)	Urobilinogen
Lactate dehydrogenase (LDH)	Monocyte count (absolute and %)	
Lipase	Neutrophil count (absolute and %)	Pregnancy test (if applicable)
Magnesium		
Phosphorus	Complete blood count with differential (CBC/diff)	
Potassium		
Protein (albumin and total)		*Special assessment
Sodium		Serum pregnancy test if a positive urine pregnancy test
Triglycerides		

APPENDIX 2. CONTRACEPTION GUIDANCE

The guidance below applies for development products with potential or unknown reproductive toxicity (for products in clinical trials, where pre-clinical data are indicative of risk or have not yet been completed).

Female subjects of childbearing potential who are heterosexually active must consent to use a highly effective method of contraception as listed below to prevent pregnancy over the time period required for product levels to decrease to a concentration that is no longer considered relevant for human teratogenicity/fetotoxicity. This time period is generally determined by the pharmacokinetic properties of the study product and non-clinical reproductive toxicity data and is defined in the protocol or product Investigator Brochure.

Highly effective contraceptive methods are those with a failure rate of less than 1% per year when used consistently and correctly.

Female subjects of childbearing potential are defined as having reached menarche prior to or during the study. Females not of childbearing potential include those who have not experienced menarche, are postmenopausal (defined as having no menses for at least 12 months without an alternative medical cause) or are permanently sterile due to having total hysterectomy, bilateral salpingectomy, or bilateral oophorectomy.

• A high follicle stimulating hormone (FSH) level in the postmenopausal range may be used to confirm a postmenopausal state in women not using hormonal contraception or hormonal replacement therapy. However, in the absence of 12 months of amenorrhea, a single FSH measurement is insufficient and multiple measurements are needed.

Male subjects who are heterosexually active with female partners of childbearing potential must consent to use one of the highly effective methods of contraception listed below to prevent pregnancy over the period defined in the protocol or product Investigator Brochure. The time period required is generally determined by the pharmacokinetic properties of the study product and non-clinical reproductive toxicity data, plus 90 days for a full sperm cycle.

Highly effective methods of contraception (CTFG, 2020) include:

- Combined (estrogen and progestogen containing) hormonal contraception associated with inhibition of ovulation (eg, oral, intravaginal, transdermal)
- Progestogen-only hormonal contraception associated with inhibition of ovulation (eg, oral, injectable, implantable)
- Intrauterine device or intrauterine hormone-releasing system
- Bilateral tubal occlusion
- Male sterilization, also called vasectomy
- Sexual abstinence is defined as refraining from heterosexual intercourse during the entire study period associated with risk of the Investigational Product (IP), other study treatments or procedures

The reliability of sexual abstinence should be evaluated in relation to the duration of the study and the preferred and usual lifestyle of the subject.

Abstinence is only considered a highly effective method of contraception if practiced consistently for the entire period of exposure to IP or other study treatments.

Periodic abstinence (calendar, symptothermal, postovulation methods), withdrawal (coitus interruptus), spermicides only, and lactational amenorrhea methods are not acceptable methods of contraception.

Note: Barrier methods (such as a condom used with or without a spermicide or a diaphragm or cervical cap used with a spermicide) used alone are NOT highly effective contraception methods.

Additional Requirement: If IP is an advanced therapy medicinal product (eg, gene therapy), a condom with spermicide is also required to be used by all sexually active males in the study in order to prevent potential transmission of the vector via seminal fluid.

